## 7. Sample Size

Sample size calculations were performed to detect a non-inferiority margin of 4.5 points on the FACT-L at week 24, assuming a standard deviation of 17.5 points and a between-group difference of 0 points. 188 patients per group were required to achieve 80% power with a one-sided significance level of 0.05. To account for an anticipated 36% rate of missing data at week 24 due to loss-to-follow-up, withdrawal, or death, enrollment of 255 per group (510 total) was planned.

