7.4. Sample Size and Power Calculation

The primary endpoint of the study is to establish that stepped PC is non-inferior to early integrated PC in the change in QOL, as measured by the FACT-L at week-24. Although the primary endpoints in our previous studies assessed the change in FACT-L from baseline to week-12, we chose to focus on QOL at 24 weeks as the life-expectancy of patients with advanced lung cancer has improved over the last few years. Thus, examining QOL at 12 weeks may overlook important differences between groups as the disease progresses. In our most recent trial of early integrated PC versus standard oncology care, we observed a 7.5-point difference in the FACT-L at week-24 favoring the integrated PC group. Thus, we chose a conservative non-inferiority margin of 4.5 points, which is slightly less than 50% of the previously observed advantage with early integrated PC compared to oncology care alone. As a 6-point difference in FACT-L score is considered the lowest range of a clinically meaningful difference, our non-inferiority margin would not reach the threshold of clinically meaningful difference in QOL.⁵⁵ With

188 patients per group, we will have >80% power to establish the non-inferiority of stepped PC compared to early integrated PC on the FACT-L with a one-sided alpha of 0.05, and a non-inferiority margin of 4.5 points. We are currently observing 35% missing data across sites at 24 weeks, primarily due to progressive illness or death. Therefore, we increased our sample size to 255 per group to ensure we have adequate power to assess for non-inferiority of stepped PC.

Our study also has adequate power to assess for non-inferiority of stepped PC compared to early integrated PC in EOL communication and hospice length-of-stay. With a sample size of 510, we will have >80% power, with a one-sided alpha of 0.05, to reject the hypothesis that patient-reported EOL communication with stepped PC would be 10% lower than early integrated PC, assuming that the rate of EOL communication in the early integrated PC group is 30% (based on our recent trial). With this sample size, we will also have >80% power to establish the non-inferiority of stepped PC compared to early integrated PC in hospice length-of-stay with a one-sided alpha of 0.05, and a non-inferiority margin of 7 days. We were conservative with our power estimations by using the highest observed standard deviation for all outcomes from prior studies.

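### 255 patients per arm do not leave 188 evaluable at the stated 35–36% missing data; the plan's own inputs give about 75% power, not 80%

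*SAP*

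**What the plan says.** SAP section 7 gives the full set of inputs. The margin comes first: "Sample size calculations were performed to detect a non-inferiority margin of 4.5 points on the FACT-L at week 24". The other two inputs are an SD of 17.5 and no true difference between the arms. On that basis, "188 patients per group were required to achieve 80% power with a one-sided significance level of 0.05". The next sentence makes the allowance for incomplete follow-up: "To account for an anticipated 36% rate of missing data at week 24", which it attributes to loss to follow-up, withdrawal or death, "enrollment of 255 per group (510 total) was planned".

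Protocol section 7.4 follows the same path with slightly different figures. It says that with "188 patients per group, we will have >80% power to establish the non-inferiority of stepped PC compared to early integrated PC on the FACT-L", again at a one-sided 0.05 level and a margin of 4.5 points. It then reports "We are currently observing 35% missing data across sites at 24 weeks" and concludes: "Therefore, we increased our sample size to 255 per group to ensure we have adequate power".

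Neither document shows how 188 became 255.

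Two other parts of the plan determine what missing data do to the primary test. SAP section 8 (Missing Data) says that the primary analyses use the data that are available and impute nothing. SAP section 9 (Primary Outcome) fits a linear regression of week-24 FACT-L on group, baseline FACT-L and the stratification factors. A patient without a week-24 score therefore contributes nothing to the primary comparison.

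**The concern.** The 188 is the number of patients per arm who must have a week-24 FACT-L. If a fraction *d* will be missing, the number to enrol is 188/(1 − *d*). The planned 255 is close to 188 × (1 + *d*) instead. That product is always too small, and at *d* near one third the gap is large.

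The primary non-inferiority test is what is at stake. If stepped PC fails to meet the margin, readers will interpret the failure against the planned power. They would take the trial as having a 20% chance of missing true equivalence, when the plan's own assumptions put that chance near 25%. The sample-size justification appears in both governing documents, and both give a reader the impression that the missing data have been covered.

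**Working it through.** **Inputs**

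- Margin 4.5 points, SD 17.5, true difference 0, one-sided alpha 0.05, target power 80%: SAP 7.
- Evaluable number 188 per group: SAP 7 and protocol 7.4.
- Missing at week 24: 36% (SAP 7), 35% (protocol 7.4).
- Enrolment 255 per group, 1:1 allocation: SAP 2 and 7, protocol 7.4.

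**Step 1. Reproduce the 188.**

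n = 2 × 17.5² × (1.645 + 0.842)² / 4.5² = 187.0 per group. The unrounded value is 187.003, so it rounds up to 188.

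Power = Φ(4.5 / (17.5 × √(2/n)) − 1.645). At n = 188 this is Φ(2.493 − 1.645) = 80.2% (80.1% by the noncentral t). The plan's 188 is confirmed.

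**Step 2. Try to reproduce the 255.**

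| Missing rate | 188/(1 − d) | 188 × (1 + d) |
|---|---|---|
| 36% (SAP) | 293.75, so 294 | 255.7 |
| 35% (protocol) | 289.2, so 290 | 253.8 |

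Division does not give 255 at either rate. Multiplication gives values on either side of it. The ratio used is 255/188 = 1.356.

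**Step 3. Find the missing rate that 255 does cover.**

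1 − 188/255 = 26.3%. Neither document mentions a rate this low.

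**Step 4. Evaluable patients and power at 255 per group.**

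| Missing rate | Evaluable per group | Power (normal) | Power (noncentral t) |
|---|---|---|---|
| 36% | 255 × 0.64 = 163.2 | Φ(2.323 − 1.645) = 75.1% | 75.0% |
| 35% | 255 × 0.65 = 165.75 | Φ(2.341 − 1.645) = 75.7% | 75.5% |

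**Step 5. What would restore 80%.**

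Solving the power formula for the SD gives 4.5 / (2.487 × √(2/n)): 16.35 at 163.2 per group and 16.48 at 165.75. If 17.5 is an unadjusted SD, adjusting for baseline multiplies it by √(1 − r²), where r is the correlation between baseline and week-24 FACT-L. The r needed is √(1 − (16.35/17.5)²) = 0.36, or 0.34 at the lower missing rate.

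The documents do not give r. With r as an assumption, power at 163 to 166 per group is:

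| r | Power |
|---|---|
| 0.2 | 76.6% to 77.2% |
| 0.3 | 78.5% to 79.1% |
| 0.5 | 85.0% to 85.5% |
| 0.6 | 89.6% to 90.0% |

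**The case against.** The best defence is that true power may well be adequate. The primary model adjusts for baseline FACT-L, and a modest correlation is enough to recover 80%. Protocol 7.4 also says that its power estimates took the largest SD seen in the earlier studies, so 17.5 may be pessimistic. An SD about 6% to 7% smaller would close the gap.

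This limits the consequence but does not correct the calculation. Neither document gives a correlation, says whether 17.5 is a raw or a residual SD, or claims a gain from adjustment. If 17.5 already reflects adjustment, nothing is left to recover from that source. The remark about the largest SD gives no smaller value, so the size of any cushion is unknown.

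Three smaller points are fair:

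- The multiplication by 1.36 is inferred. No formula is printed, and 255.7 would normally be rounded up to 256. The shortfall does not depend on how 255 was reached.
- Both documents attach the 80% figure to 188 per group. For 255, the protocol says only that power is adequate and the SAP says only that missing data are accounted for. The implication that 80% is preserved is nevertheless plain.
- SAP section 2 reports that 510 patients were already enrolled. The type I error, the margin and the decision rule based on the 90% confidence interval are unaffected, and that interval will show the precision achieved. This rules out a larger trial as the remedy, but the stated power still needs correcting.

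**Conclusion.** The concern holds. The 188 is right, and the step from 188 to 255 is wrong as written. At the plan's own missing rates, 255 per arm gives 163 to 166 evaluable patients per arm, which is 22 to 25 fewer than required. Power is then 75.1% to 75.7% and type II error 24.3% to 24.9%. Keeping 188 evaluable would have needed 290 to 294 per arm (580 to 588 in total).

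These figures rest on the SAP's SD of 17.5, a true difference of zero, a one-sided 0.05 test, and an analysis of observed week-24 scores with no credit for baseline adjustment. Such credit could bring power back to 80% or above, but that would be a new argument with its own stated assumptions. The 35% and 36% rates also need to be reconciled, although the choice between them moves power by only about 0.6 points.

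**What to change.** Correct the statement in protocol 7.4 and SAP 7, using one missing-data rate in both. Either of two forms would do:

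1. Restate on the existing inputs. At 36%, for example: *Enrolling 255 per group with 36% of week-24 data missing is expected to leave about 163 evaluable patients per group and about 75% power, assuming an SD of 17.5.* At 35%, the evaluable number is about 166 and power about 76%.
2. Recompute power for the planned baseline-adjusted model at the expected evaluable number. Say whether 17.5 is the raw or the residual SD, give the assumed correlation between baseline and week 24 and its source, and show power over a range of correlations.

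The second form matches the analysis that will be run and is preferable if the earlier trials can supply the correlation. If they cannot, use the first.

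The cost is about two sentences in each document. In the SAP they could go in the existing addendum. Enrolment, endpoint, margin and analysis do not change. Under the first form, the stated power becomes less favourable.

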## 8. General Statistical Considerations

### *Statistical Software*

All statistical analyses will be performed using SAS (SAS Institute Inc., NC, USA) and R (R Foundation for Statistical Computing, Vienna, Austria).

### *Analysis Population*

The primary analyses will be conducted according to the intention-to-treat principle. All randomized patients will be included and analyzed in the group to which they were initially randomized, regardless of intervention adherence. If there is considerable non-adherence to the randomized intervention, we will conduct additional *post hoc* per-protocol analyses (e.g., using causal inference g-methods, such as inverse probability weighting) to assess whether study results are sensitive to non-adherence to the assigned intervention group.

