7.5.5. Handling of Missing Data

The analyses will initially focus on patients who completed the 24-week assessment to compare stepped PC with early integrated PC without imposing assumptions about missing data. We will also use the intention-to-treat principle with all randomized subjects, conducting sensitivity analyses to explore how various assumptions about missing data and differences between completers and non-completers affect the estimated outcomes. If data appear to be missing at random, we will employ multiple imputation methods. However, if we find that participants do not complete assessments due to progressive illness, suggesting missing data are not random, we will employ pattern mixture modeling or terminal decline joint modeling approach to address missing data.

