### *Missing Data*

Primary analyses will include available data without imputation of missing data. The characteristics of patients who complete versus do not the week 24 survey will be compared descriptively. Sensitivity analyses will explore how different assumptions about the missing data mechanisms affect estimated outcomes. These sensitivity analyses may include multiple imputation, terminal decline joint modeling, or partially conditional models, which provide estimates of the mean conditional on being alive and observed at each timepoint.

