## **9. Statistical Analysis**

### *Primary Outcome*

The primary outcome is patient-reported quality of life at week 24, as measured by the FACT-L. The difference in week 24 means between intervention groups will be estimated using a linear regression model with group assignment (stepped PC vs early integrated PC) and baseline FACT-L score, as well as randomization stratification factors, as main effects. Using the pre-specified non-inferiority margin of 4.5 points, non-inferiority of stepped PC will be established if the lower limit of the 90% confidence interval (CI) for the estimated difference in means is greater than -4.5. The corresponding p-value for non-inferiority will be calculated using a one-sided test of the estimated difference in means against a null value of -4.5 with a significance level of 0.05. Model-based estimates of the mean with 95% CI in each group, the difference in means between groups and its 90% CI, and the p-value will be reported.

To accompany the approach described above, we will also use a linear mixed effects regression model to estimate the difference in week 24 means between intervention groups. This model will utilize FACT-L scores at baseline, week 12, and week 24, with estimation via maximum likelihood. The model will include fixed effects for group assignment (stepped PC vs early integrated PC), time from baseline (in weeks), time-by-group interaction, and randomization stratification factors, as well as random intercepts for each patient. A contrast will be used to estimate the difference in means at week 24, and this estimate will be evaluated for non-inferiority in the same manner described above. This will be reported as a sensitivity analysis for evaluating non-inferiority for the primary outcome.

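### The SAP says the primary analysis includes all randomized patients, but the week-24 regression keeps only those with a week-24 score (about 64%), and no fixed analysis tests departures from missing at random

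*SAP*

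**What the plan says.** SAP section 8, Analysis Population, places the primary analyses under the intention-to-treat principle: "All randomized patients will be included and analyzed in the group to which they were initially randomized".

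Two other SAP passages determine who actually enters the primary result. Section 8, Missing Data: "Primary analyses will include available data without imputation of missing data". Section 9, Primary Outcome, defines the estimator as follows, with week-24 FACT-L as the response: "linear regression model with group assignment (stepped PC vs early integrated PC) and baseline FACT-L score, as well as randomization stratification factors, as main effects".

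Protocol 7.5.5 is more open about the population: "The analyses will initially focus on patients who completed the 24-week assessment to compare stepped PC with early integrated PC". It adds that this is done "without imposing assumptions about missing data", and then continues: "We will also use the intention-to-treat principle with all randomized subjects, conducting sensitivity analyses". It goes on to commit to multiple imputation if data look missing at random, and to pattern-mixture or terminal-decline joint modelling if patients miss assessments because of progressive illness.

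SAP section 9 also commits to a linear mixed model as a sensitivity analysis for the primary outcome, judged against the same limit: "This model will utilize FACT-L scores at baseline, week 12, and week 24, with estimation via maximum likelihood". Its fixed effects are group, time in weeks, their interaction and the strata, with a random intercept per patient.

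For everything else the SAP's wording is permissive: "These sensitivity analyses may include multiple imputation, terminal decline joint modeling, or partially conditional models".

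**The concern.** A regression with week-24 FACT-L as the response drops every patient who lacks that score, so the Analysis Population sentence is not true of the primary result. A report that copied it would present a completer comparison as one that included all randomized patients.

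The Protocol's statement that the completer comparison makes no missing-data assumption is also wrong. For that comparison to speak for all randomized patients, missingness must be ignorable given arm, baseline FACT-L and strata. Protocol 7.4 gives a reason for doubt, since it attributes the loss mainly to progressive illness or death.

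The direction matters in a non-inferiority trial whose test arm has less scheduled contact. If stepped patients who deteriorate are the ones who go unobserved, and early integrated patients less so, the comparison leans towards non-inferiority. The documents do not show that this happens. The plan contains no fixed analysis that would show how far it would have to go before the conclusion changed.

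**Working it through.** **Inputs.** SAP 7: margin 4.5, SD 17.5, true difference 0, one-sided 0.05, 80% power, 188 per group, 36% missing at week 24, 255 per group (510 total). Protocol 7.4: 35% missing. SAP 9: non-inferiority if the lower 90% limit exceeds -4.5. SAP 4: baseline measures completed before randomization.

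**1. The plan's own figure.** n = 2 × SD² × (z₀.₉₅ + z₀.₈₀)² / margin² = 2 × 17.5² × (1.645 + 0.842)² / 4.5², which is just over 187 and rounds up to 188. Power at 188 per group is 80.2%. The SAP figure reproduces.

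**2. Who is in the primary regression.** 255 × (1 - 0.36) = 163.2 per group, so about 326 of 510 are in and 510 × 0.36 ≈ 184 are out. At 35% missing it is about 166 per group.

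**3. Who is in the mixed model.** A maximum-likelihood mixed model keeps any patient with at least one score, and baseline precedes randomization. In a simulated 510-patient data set (36% missing at week 24, an assumed 22% at week 12) it kept 510 of 510. The completer regression kept 315. So one all-randomized analysis is fixed. It is valid under missing at random, and also depends on time entered in weeks (no categorical visit is stated) and on random intercepts only.

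**4. What is fixed beyond missing at random.**

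| | Protocol 7.5.5 | SAP 8, Missing Data |
|---|---|---|
| Missingness due to progressive illness | Pattern-mixture or terminal-decline joint modelling will be used | Terminal-decline joint modelling is one of three options that may be used; pattern-mixture is not listed |
| Model, parameters, range | Not given | Not given |

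Protocol 7.4's description of the missing data points to the Protocol's own condition being met, yet the later document makes the response optional.

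**5. Room before the margin.** With 163 per group and an observed difference of 0:
- SE = 17.5 × √(2/163) = 1.94
- 90% half-width = 1.645 × 1.938 = 3.19, so the lower limit is -3.19
- slack = 4.5 - 3.19 = 1.31 points

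**6. Tipping gap.** Let m be the unobserved share of the target population. The overall difference is (1 - m) × observed + m × unobserved. With an observed difference of 0 and the completer SE held fixed, the lower limit reaches -4.5 when unobserved stepped patients score 1.31/m points below unobserved early integrated patients. If deaths leave the target population, m is the share alive but unobserved among those alive. The documents do not split the 36%, so the death shares below are assumptions, taken as equal in both arms.

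| Share of missing that are deaths | m | Tipping gap (points) |
|---|---|---|
| Not separated, all 36% counted | 0.36 | 3.6 |
| One-third | 0.24/0.88 = 0.27 | 4.8 |
| One-half | 0.18/0.82 = 0.22 | 6.0 |
| Two-thirds | 0.12/0.76 = 0.16 | 8.3 |

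At 35% missing, all counted, the gap is about 3.8. For scale, Protocol 7.4 takes 6 points as the lowest clinically meaningful FACT-L difference.

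**The case against.** The strongest reply is that the plan is more open and more complete than one sentence suggests. The Analysis Population paragraph mainly states an allocation rule: analyse as randomized, whatever the adherence. The same section declares the available-data basis and promises a comparison of week-24 completers with non-completers. The flow diagram will show exclusions by group, and the sample-size section states the 36%. This stands. The sentence is inaccurate, but nothing is hidden.

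A reader might infer that no all-randomized check is fixed at all. The documents do not support that. The mixed model in SAP 9 is a firm commitment, uses baseline, week-12 and week-24 scores, and is judged against -4.5. Nor is the Protocol silent on non-random missingness; its commitment is conditional and unspecified.

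A reader might also infer a particular inflation of the error rate. One can construct a case: a completer difference of -2.5 with a true overall difference of -4.5 needs a gap of (4.5 - 0.64 × 2.5)/0.36 ≈ 8.1 points among the missing, and false non-inferiority would then be about 27%. Nothing in the documents supports that pair. The 8.1 points exceed the 7.5-point week-24 difference that Protocol 7.4 reports between integrated PC and oncology care alone, whereas here both arms receive PC and stepped patients can step up.

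Finally, the 3.6-point gap counts the dead among patients to be given a score. Once deaths are separated, the gap is larger in every case computed, so 3.6 should not be quoted alone.

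**Conclusion.** The point holds in three parts. The SAP's Analysis Population sentence is wrong for the primary regression, which is expected to use about 64% of randomized patients. The Protocol's claim that the completer comparison is free of missing-data assumptions is wrong. The SAP fixes no analysis that departs from missing at random, although the Protocol undertakes to use one under a condition that its own account of the missing data suggests is met.

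The size is moderate and uncertain. At an observed difference of 0, an arm gap among unobserved patients of about 3.6 points (all missing counted) or 4.8 to 8.3 points (one-third to two-thirds of the missing being deaths) would remove non-inferiority. These figures rest on SD 17.5, 36% missing, equal missingness and deaths by arm, and the completer SE. They illustrate sensitivity; they are not evidence that bias is present or that it favours the stepped arm. The primary estimator and margin need not change.

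**What to change.** 1. Reword SAP 8, Analysis Population, so that the primary population is randomized patients with a scoreable week-24 FACT-L, analysed as randomized. Delete from Protocol 7.5.5 the phrase claiming that no missing-data assumption is made.
2. In the SAP 9 mixed model, specify visit as categorical, so that the week-24 contrast does not lean on a straight-line trend.
3. Commit to one delta-adjusted (pattern-mixture) multiple imputation. Apply delta to stepped-arm patients who are alive but unobserved at week 24, over a range stated in advance; 0 to -10 points would span every gap in the table. Report the delta at which the lower 90% limit crosses -4.5. When the observed difference is 0 and imputation under missing at random shows no arm difference, this delta corresponds to the tipping gap above.
4. Show deaths before week 24 by arm beside it, because a comparison among patients alive at week 24 is not fully protected by randomization.

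Report the tipping delta for judgement. A pass/fail rule, for example at the 6-point meaningful difference, has no source in the plan and would add a hurdle to the agreed test.

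The cost is a little programming and no new data. The SAP already has a dated addendum for such changes; if outcomes have been seen by then, the entry should say so. The downside is that the non-inferiority claim may need more cautious wording.
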